10.3.2. Treatment States

Assessments and events will be classified according to time of occurrence relative to the start and/or stop date of the study treatment.

10.3.2.1. Treatment States for Concomitant Medication Data

Treatment State	Definition
Pre-Treatment	Medication End Date \leq Study Treatment Start Date
On-Treatment	Study Treatment Start Date \leq Conmed Start Date \leq Study Treatment Stop Date Study Treatment Start Date \leq Conmed End Date
Post-Treatment	ConMed Start Date > Study Treatment Stop Date

NOTES:

- If the study treatment stop date is missing then the assessment will be considered to be On-Treatment

10.3.2.2. Treatment States for AE Data

Treatment State	Definition
Pre-Treatment	AE Start Date < Study Treatment Start Date
On-Treatment	If AE onset date is on or after treatment start date & on or before treatment stop date. Study Treatment Start Date \leq AE Start Date \leq Study Treatment Stop Date
Post-Treatment	If AE onset date is after the treatment stop date. AE Start Date > Study Treatment Stop Date
Onset Time Since 1 st Dose (Days)	If Treatment Start Date > AE Onset Date = AE Onset Date - Treatment Start Date If Treatment Start Date \leq AE Onset Date = AE Onset Date - Treatment Start Date + 1 Missing otherwise.
Duration (Days)	AE Resolution Date – AE Onset Date + 1
Drug-related	If relationship is marked 'YES' on PIMS OR value is missing.

NOTES:

- If the study treatment stop date is missing then the AE will be considered to be On-Treatment.

10.4. Appendix 4: Data Display Standards & Handling Conventions

10.4.1. Study Treatment & Sub-group Display Descriptors

Treatment Group Descriptions			
RandAll NG		Data Displays for Reporting	
Code	Description	Description ^[2]	Order ^[1]
A	Placebo inhaled single dose	Placebo	1
B	50ug GSK2292767 inhaled single dose	50ug OD	2
C	Dose Level 2 GSK2292767 inhaled single dose	100ug OD	3
D	Dose Level 3 GSK2292767 inhaled single dose	200ug OD	4
E	Dose Level 4 GSK2292767 inhaled single dose	500ug OD	5
F	Dose Level 5 GSK2292767 inhaled single dose	1000ug OD	6
G	Dose Level 6 GSK2292767 inhaled single dose	2000ug OD	7
H	Placebo inhaled repeat dose	Placebo	1
I	Dose Level 7 GSK2292767 inhaled repeat dose	XXXXug OD	2

NOTES:

1. Order represents treatments being presented in TFL, as appropriate.
2. Replace X's with the actual agreed dose for the cohort and period.

10.4.2. Baseline Definition & Derivations

10.4.2.1. Baseline Definitions

For all endpoints the baseline value will be the latest pre-dose assessment. For Part A, baseline definitions are applicable to each period. Note that no baseline sputum assessments are planned for Part A so any comparisons will be purely versus placebo at the corresponding timepoints.

10.4.2.2. Derivations and Handling of Missing Baseline Data

Definition	Reporting Details
Change from Baseline	= Post-Dose Visit Value – Baseline
% Change from Baseline	= 100 x [(Post-Dose Visit Value – Baseline) / Baseline]

NOTES:

- Unless otherwise specified, the baseline definitions specified in Section 10.4.2. Baseline Definitions will be used for derivations for endpoints / parameters and indicated on summaries and listings.
- Unless otherwise stated, if baseline data is missing no derivation will be performed and will be set to missing.
- The baseline definition will be footnoted on all change from baseline displays.

10.4.3. Reporting Process & Standards

Reporting Process	
Software	

 • The currently supported versions of SAS software (Version 9.4) will be used. 	
Reporting Area	
HARP Server	:: UK1SALX00175.corpnet2.com
HARP Area	Two reporting efforts will be set up for this study, 1 for Part A (Final_01) and 1 for Part B (Final_02).
QC Spreadsheet	: ARPROD\ GSK 2292767 \202062\Final\Documents
Analysis Datasets	

 • Analysis datasets will be created according to Integrated Data Standards Library. 	
Generation of RTF Files	

 • RTF files will be generated for all tables 	

Reporting Standards	
General	

 • The current GSK Integrated Data Standards Library (IDSL) will be applied for reporting, unless otherwise stated: 
 ○ 4.03 to 4.23: General Principles ○ 5.01 to 5.08: Principles Related to Data Listings ○ 6.01 to 6.11: Principles Related to Summary Tables ○ 7.01 to 7.13: Principles Related to Graphics 	
Formats	

 • All data will be reported according to the actual treatment the subject received unless otherwise stated. • GSK IDSL Statistical Principles (5.03 & 6.06.3) for decimal places (DP's) will be adopted for reporting of data based on the raw data collected. • Numeric data will be reported at the precision collected on the eCRF. • The reported precision from non eCRF sources will follow the IDSL statistical principles but may be adjusted to a clinically interpretable number of DP's. 	

Reporting Standards	
Planned and Actual Time	

 Reporting for tables, figures and formal statistical analyses: 
 Planned time relative to dosing will be used in figures, summaries, statistical analyses and calculation of any derived parameters, unless otherwise stated. The impact of any major deviation from the planned assessment times and/or scheduled visit days on the analyses and interpretation of the results will be assessed as appropriate. Reporting for Data Listings: 
 Planned and actual time relative to study drug dosing will be shown in listings (Refer to IDSL Statistical Principle 5.05.1). Unscheduled or unplanned readings will be presented within the subject's listings. Visits outside the protocol defined time-windows (i.e. recorded as protocol deviations) will be included in listings but omitted from figures, summaries and statistical analyses. 	
Unscheduled Visits	

 Unscheduled visits will not be included in summary tables. Unscheduled visits will not be included in figures. All unscheduled visits will be included in listings. 	
Descriptive Summary Statistics	
Continuous Data	Refer to IDSL Statistical Principle 6.06.1
Categorical Data	N, n, frequency, %
Reporting of Pharmacokinetic Concentration Data	
Descriptive Summary Statistics	Refer to IDSL Statistical Principle 6.06.1 Assign zero to NQ values (Refer to GUI_51487 for further details)
Reporting of Pharmacokinetic Parameters	
Descriptive Summary Statistics (Log Transformed)	N, n, geometric mean, 95% CI of geometric mean, standard deviation (SD) of logged data and between and or within geometric coefficient of variation (CV _{b/w} (%)) will be reported. [1] $CV_b (\%) = \sqrt{(\exp(SD^2) - 1) * 100}$ (SD = SD of log transformed data) [2] $CV_w (\%) = \sqrt{(\exp(MSE) - 1) * 100}$ (MSE = mean square error from mixed effect model of loge-transformed data).
Parameters Not Being Log Transformed	Tmax
Summary Tables	All provided PK parameters will be summarised except Lamz, lamzUL, LamzLL, LamzNP and AUC % extrapolated area (if calculated).
Listings	Additionally, include the first point, last point and number of points used in the determination of lambda _z for listings.
Graphical Displays	

 Refer to IDSL Statistical Principles 7.01 to 7.13. All graphics will be done using the SGPLOT/SGPANEL/SG template procedures. Where possible, n's will be displayed in summary plots. 	

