10.11.4. Safety Tables

Safety : Tables					
No.	Population	IDSL / TST ID / Example Shell	Title	Programming Notes	Deliverable [Priority]
Part A (Single Dose Escalation): Exposure					
2.101	Safety (Part A)	EX1	Summary of Extent of Exposure to Study Treatment (Single Dose)		SAC
Part B (Repeat Dose): Exposure					
2.201	Safety (Part B)	EX1	Summary of Extent of Exposure to Study Treatment (Repeat Dose)		SAC
Part A (Single Dose Escalation): Adverse Events					
2.102	Safety (Part A)	CP_AE1x	Summary of All Adverse Events by System Organ Class (Single Dose)	Include total column.	SAC
2.103	Safety (Part A)	CP_AE1x	Summary of Drug-Related Adverse Events by System Organ Class (Single Dose)	Include total column.	SAC

Safety : Tables					
No.	Population	IDSL / TST ID / Example Shell	Title	Programming Notes	Deliverable [Priority]
2.104	Safety (Part A)	AE15/EMA_AE	Summary of Common ($\geq 5\%$) Non-serious Adverse Events by System Organ Class and Preferred Term (Number of Subjects and Occurrences, Single Dose)		SAC
Part B (Repeat Dose): Adverse Events					
2.202	Safety (Part B)	CP_AE1p	Summary of All Adverse Events by System Organ Class (Repeat Dose)	Include total column.	SAC
2.203	Safety (Part B)	CP_AE1p	Summary of Drug-Related Adverse Events by System Organ Class (Repeat Dose)	Include total column.	SAC
2.204	Safety (Part B)	AE15	Summary of Common ($\geq 5\%$) Non-serious Adverse Events by System Organ Class and Preferred Term (Number of Subjects and Occurrences, Repeat Dose)		SAC
Part A (Single Dose Escalation): Labs					
2.105	Safety (Part A)	LB1	Summary of Chemistry Changes from Baseline by Visit (Single Dose)		SAC
2.106	Safety (Part A)	LB3	Summary of Emergent Chemistry Results by Potential Clinical Importance Criteria (Single Dose)		SAC
2.107	Safety (Part A)	LB1	Summary of Haematology Changes from Baseline by Visit (Single Dose)		SAC
2.108	Safety (Part A)	LB3	Summary of Emergent Chemistry Results by Potential Clinical Importance Criteria (Single Dose)		SAC

Safety : Tables					
No.	Population	IDSL / TST ID / Example Shell	Title	Programming Notes	Deliverable [Priority]
Part B (Repeat Dose): Labs					
2.205	Safety (Part B)	LB1	Summary of Chemistry Changes from Baseline by Visit (Repeat Dose)		SAC
2.206	Safety (Part B)	LB3	Summary of Emergent Chemistry Results by Potential Clinical Importance Criteria (Repeat Dose)		SAC
2.207	Safety (Part B)	LB1	Summary of Haematology Changes from Baseline by Visit (Repeat Dose)		SAC

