2.208	Safety (Part B)	LB3	Summary of Emergent Chemistry Results by Potential Clinical Importance Criteria (Repeat Dose)		SAC
Part A (Single Dose Escalation): ECGs					
2.109	Safety (Part A)	EG2	Summary of Change from Baseline in ECG Values by Visit. (Single Dose)		SAC
2.110	Safety (Part A)	EG1	Summary of Maximum Emergent QTc Values by Category. (Single Dose)		SAC
2.111	Safety (Part A)	EG1	Summary of 12-Lead ECG Findings (Single Dose)		SAC
Part B (Repeat Dose): ECGs					
2.209	Safety (Part B)	EG2	Summary of Change from Baseline in ECG Values by Visit. (Repeat Dose)		SAC
2.210	Safety (Part B)	EG1	Summary of Maximum Emergent QTc Values by Category. (Repeat Dose)		SAC

Safety : Tables					
No.	Population	IDSL / TST ID / Example Shell	Title	Programming Notes	Deliverable [Priority]
2.211	Safety (Part B)	EG1	Summary of 12-Lead ECG Findings (Single Dose)		SAC
Part A (Single Dose Escalation): Vital Signs					
2.112	Safety (Part A)	VS1	Summary of Change from Baseline in Vital Signs by Visit (Single Dose)	Include the Respiration Rate and Tympanic Temperature	SAC
Part B (Repeat Dose): Vital Signs					
2.212	Safety (Part B)	VS1	Summary of Change from Baseline in Vital Signs by Visit (Repeat Dose)	Include the Respiration Rate and Tympanic Temperature	SAC
Part A (Single Dose Escalation): Spirometry					
2.113	Safety (Part A)	PD_PFT1	Summary of Lung Function Data (Single Dose)		SAC
Part B (Repeat Dose): Spirometry					
2.213	Safety (Part B)	PD_PFT1	Summary of Lung Function Data (Repeat Dose)		SAC

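### Section 10.4.3 keeps unscheduled and deviating out-of-window visits out of the summary tables, with no exception for the maximum-QTc and emergent-PCI tables, which can therefore understate the worst values and disagree with the listings

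*SAP*

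**What the plan says.** All of the relevant handling rules are in the SAP.

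- **Unscheduled visits (Section 10.4.3).** "Unscheduled visits will not be included in summary tables". The same block excludes them from figures and then says "All unscheduled visits will be included in listings".
- **Out-of-window visits (Section 10.4.3, planned and actual time).** "Visits outside the protocol defined time-windows (i.e. recorded as protocol deviations) will be included in listings but omitted from figures, summaries and statistical analyses".
- **Extra readings (same block).** "Unscheduled or unplanned readings will be presented within the subject's listings". Nothing says whether they also enter tables.
- **Time basis (same block).** "Planned time relative to dosing will be used in figures, summaries, statistical analyses and calculation of any derived parameters, unless otherwise stated".
- **Withdrawn subjects (Section 10.6.1).** Planned data are what enters summaries, unless otherwise specified.
- **Repeat values and any-visit counts (Section 10.5.1).** Several measurements at one time point are averaged before summary statistics are derived. A subject with both high and low values at any visit after baseline is counted in both categories of the any-visit row, and this extends to the PCI tables.
- **The worst-case tables (Section 10.11.4).** Tables 2.110 and 2.210 are each titled "Summary of Maximum Emergent QTc Values by Category". Tables 2.106, 2.108, 2.206 and 2.208 summarise emergent results against PCI criteria. The programming-note cells of all six are empty.
- **The listings (Sections 10.11.11 and 10.11.12).** Listings 14 to 21 and 37 to 44 show laboratory, vital-sign and ECG values of PCI, and all such data for subjects who had one.

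**The concern.** By-visit summaries need a common time axis, so leaving unscheduled values out of them is sound. A maximum or an ever-crossed count has no time axis. It asks whether something happened at all after dosing, and an incomplete set of values gives an incomplete answer.

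The values left out are not a random subset. An unscheduled visit may be prompted by a symptom or by an abnormal result, so its values may be among the more extreme. Safety and tolerability is the primary objective, it is summarised descriptively, and these tables are where maximum QTc and laboratory PCI counts are shown by treatment. If they leave out values that the listings contain, the report can give two answers for one criterion, and a reader of the tables alone sees the more favourable one.

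**Working it through.** The document gives no figure to reproduce. The check sets the rules side by side and asks what they do to a maximum or an ever-crossed count.

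**Step 1. Is there an exemption?** Section 10.4.3 makes none. The notes for the six tables are empty. Section 10.4.3 applies the sponsor's reporting standards (IDSL) unless otherwise stated, and the exclusion is itself stated, so a default in a standard shell cannot be presumed to override it.

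**Step 2. Direction of the effect.** For one subject with baseline held fixed, let S be the post-dose values from scheduled visits that Section 10.4.3 admits, and U the values from unscheduled visits or from out-of-window visits recorded as deviations.

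- Maximum: max(S) ≤ max(S ∪ U).
- Ever-PCI indicator: 1{some value in S meets the criterion} ≤ 1{some value in S ∪ U meets it}.

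Exclusion can therefore lower a maximum or an ever-PCI count, or leave it unchanged. It cannot raise either.

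**Step 3. Does Section 10.5.1 agree?** Its rule for PCI tables refers to any visit after baseline. Read plainly, that includes unscheduled visits, which Section 10.4.3 excludes. The SAP does not say which prevails.

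**Step 4. Extra readings within a planned visit.** The table exclusion is worded for visits. A repeat ECG on a planned day is not clearly an unscheduled visit and might instead be averaged under Section 10.5.1. For readings a < b, the mean (a + b)/2 is below b. Take the QTc PCI limit in Section 10.7.2, above 450 msec: a reading of 450 + d is hidden whenever its partner is 450 − d or lower, because the mean is then at most 450. Averaging can thus also conceal a maximum.

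**Step 5. Where could this arise?** In Section 10.1.1.1, Part A has one post-dose laboratory draw per period, at 24 h. In Section 10.1.1.2, Part B draws are pre-dose on Days 2, 4, 6, 8, 10, 12 and 14, and then on Day 15. A transient laboratory abnormality between draws would be found only by an extra sample. ECGs are denser: pre-dose and 30 minutes post-dose on each of Days 1 to 14, and again on Day 15. They are single recordings, so a confirmatory ECG is an extra reading. Part A telemetry for the first 5 h after dosing could prompt one.

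**Step 6. Size per affected subject.** The SAP gives no arm sizes. If n is the number of subjects on a treatment, one omitted subject lowers the incidence by 1/n.

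| n | Basis | 1/n |
|---|---|---|
| 12 | assumption | 8.3% |
| 6 | assumption | 16.7% |
| 5 | minimum on active drug for an escalation decision, Section 3.1 | 20.0% |

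This is conditional arithmetic. It does not say how often a subject would be affected.

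**The case against.** The strongest reply is that little is lost. Every unscheduled visit goes into listings, the PCI listings pick out the values that matter, and in small groups each such subject can be seen individually. No hypothesis test uses these tables. Escalation decisions rest on safety review during the study (Sections 3.1 and 7.1.2), not on final tables. Section 10.4.3 also commits to assessing the impact of major timing deviations. All of this stands. It limits the consequence but does not reconcile the tables with the listings.

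A reader might infer more than the document supports, in five ways.

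- *Every event-triggered reading is barred from tables.* The table rule covers visits. For extra readings within a planned visit the text is unclear, not exclusionary.
- *Every summary table is affected.* Adverse event tables are not built from visits, and only out-of-window visits recorded as deviations are dropped.
- *A Part B laboratory value from an odd day, or a Part A value after the 24 h draw, can never be counted.* Section 10.2.1 summarises non-sputum data by planned time point, so a late draw not recorded as a deviation would still enter. Section 10.6.1 mentions a follow-up visit that the schedules do not show. The protocol settles both, and it is not at hand. A Day 9 abnormality that persisted to the Day 10 draw would also be counted.
- *The undercount falls mainly on active treatment.* That needs more unscheduled visits on active, and the document has no evidence either way.
- *Safety is judged from these tables alone.* It is also shown in individual listings for every safety domain (Section 7.1.3, Table 3).

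**Conclusion.** The point holds in a limited form. As written, Section 10.4.3 lets six worst-case safety tables omit a subject's highest QTc or only PCI laboratory value when it came from an unscheduled visit or from an out-of-window visit recorded as a deviation. This conflicts with the any-visit counting rule in Section 10.5.1 and allows tables and listings to disagree. The handling of extra readings within a planned visit is unsettled, and averaging them would have a similar effect.

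The direction is certain for a fixed baseline: counts are understated or unchanged. The size is not known. One affected subject is worth 8 to 17 percentage points if there are 6 to 12 subjects per treatment, which is an assumption. The number of affected subjects, and any difference between arms, cannot be derived from the document. Because the values remain in listings, this is a defect in the counts shown in tables, not a loss of safety data. It is worth correcting before database freeze because it touches the primary objective and the correction is simple.

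**What to change.** Keep the exclusion for by-visit summaries. Add to Section 10.4.3 that maximum, emergent-PCI and any-visit-after-baseline displays use all individual post-dose values, including unscheduled readings, repeats (taken singly, not averaged) and out-of-window readings. State that for these displays this takes precedence over the averaging rule in Section 10.5.1. Put a footnote to that effect on Tables 2.106, 2.108, 2.110, 2.206, 2.208 and 2.210.

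The cost is one sentence, the footnotes and a programming filter. No new data are needed. Reported abnormality counts may become slightly less favourable, and the tables will agree with the PCI listings on which values count.

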10.5. Appendix 5: Derived and Transformed Data

10.5.1. General

Multiple Measurements at One Time Point

- Mean of the measurements will be calculated and used in any derivation of summary statistics but if listed, all data will be presented.
- If there are two values within a time window the value closest to the target day for that window will be used. If values are the same distance from the target then the mean will be taken.
- Subjects having both High and Low values for Normal Ranges at any post-baseline visits for safety parameters will be counted in both the High and Low categories of “Any visit post-baseline” row of related summary tables. This will also be applicable to relevant Potential Clinical Importance summary tables.

Study Day

- Calculated as the number of days from randomisation date:
 - Ref Date = Missing → Study Day = Missing
 - Ref Date < Randomisation Date → Study Day = Ref Date – Randomisation Date
 - Ref Date ≥ Randomisation Date → Study Day = Ref Date – (Randomisation Date) + 1

Insert as Required

- Insert as Required

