10.1. Appendix 1: Time & Events

10.1.1. Protocol Defined Time & Events

10.1.1.1. SOA – Part A (Single Dose)

Procedure	Part A (Single Dose) Treatment Period														Notes	
	Day -1	Day 1 (time relative to dosing)														
		Pre dose	0h	5m	30m	45m	1h	2h	3h	4h	6h	8h	12h	24h		
Admission to Unit	X															
Urine Drug/Alcohol breath test	X															
Urine Pregnancy test	X															
Brief Physical Exam	X														X	
Laboratory Assessments	X														X	
Meals	X								X						X	See Section 6.3.1 of protocol
12-lead ECG (single)		X				X					X			X	X	
Vital signs (single)		X			X		X				X		X	X		

Procedure	Part A (Single Dose) Treatment Period														Notes	
	Day -1	Day 1 (time relative to dosing)														
		Pre dose	0h	5m	30m	45m	1h	2h	3h	4h	6h	8h	12h	24h		
Telemetry		←-----→														Cardiac telemetry: To start approximately 1hr Pre-dose and then continuously for the first 5h post dose.
Spirometry (triplicate)		X					X									
Pharmacokinetic and Metabolite Profile Blood Sample		X		X	X	X	X	X	X	X	X	X	X	X		
Pharmacokinetic Urine Sample		X	←-----→													Only for the maximum proposed dose group if escalated up to (2000 µg).
Inhaler Training	X															
Dosing			X													
Sputum induction									X						X	
Adverse Event Review		←-----→														
Concomitant Medication Review		←-----→														
Discharge															X	

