10.1.1.2. SOA – Part B (Repeat Dose)

Procedure	Part B (Repeat Dose) Study Day																		Notes		
	D -2 or D -1	D1	D2	D3	D4	D5	D6	D7	D8	D9	D10	D11	D12	D13	D14	D15 (D14 +24h)	D16 (D14 +48h)	D17 (D14 +72h)		D18 (D14 +96h)	
Admission to Unit	X																				
Urine Drug/Alcohol	X																				
Urine Pregnancy test	X																				
Brief Physical Exam	X																				
Laboratory Assessments	X		X ¹		X ¹		X ¹		X ¹		X ¹		X ¹		X ¹	X				1. Perform assessment pre dose	
Meals	X	X	X	X	X	X	X	X	X	X	X	X	X	X	X	X				See Section 6.3.1 of protocol	
12-lead ECG (single)	X	X ²	X ²	X ²	X ²	X ²	X ²	X ²	X ²	X ²	X ²	X ²	X ²	X ²	X ²	X				2. Perform assessments pre dose and at 30 mins post dose.	
Vital signs (single)	X	X ³	X ³	X ³	X ³	X ³	X ³	X ³	X ³	X ³	X ³	X ³	X ³	X ³	X ³	X				3. Perform assessments pre dose.	
Spirometry (triplicate)	X	X ⁴	X ⁴	X ⁴	X ⁴	X ⁴	X ⁴	X ⁴	X ⁴	X ⁴	X ⁴	X ⁴	X ⁴	X ⁴	X ⁴					4. Perform assessment pre dose and 1h post dose.	
Pharmacokinetic Blood Sample		X ⁶	X ⁵	X ⁵	X ⁵	X ⁵	X ⁵	X ⁵	X ⁵	X ⁵	X ⁵	X ⁵	X ⁵	X ⁵	X ⁶	X	X ⁷	X ⁷	X ⁷	5. pre-dose and 5 min post dose. 6. pre-dose, 5 mins, 30 mins, 45 mins, 1, 2, 3, 4, 6, 8 and 12h post dose 7. If following Single dose (SD) PK analysis deemed necessary.	

Procedure	Part B (Repeat Dose) Study Day																		Notes		
	D -2 or D -1	D1	D2	D3	D4	D5	D6	D7	D8	D9	D10	D11	D12	D13	D14	D15 (D14 +24h)	D16 (D14 +48h)	D17 (D14 +72h)		D18 (D14 +96h)	
Blood Sample for Metabolic Profiling															X ⁶	X	X ⁷	X ⁷	X ⁷		
Urea Blood Sample																X					Collect sample just before bronchoscopy
Inhaler Training	X																				
Dosing		X	X	X	X	X	X	X	X	X	X	X	X	X	X						
Sputum induction	X ¹¹	X ⁸												X ⁹ 10							8. 3h post dose 9. 3h and 24h 10. Should sputum induction fail or be insufficient at any time point then the participant will be allowed to return 24h later for a further attempt to obtain an adequate sample 11. Should sputum induction fail or be insufficient then the participant will be allowed to return 24h later for a further attempt to obtain an adequate sample. Failure to produce a baseline sample will result in participant withdrawal.

CONFIDENTIAL

202062

Procedure	Part B (Repeat Dose) Study Day																		Notes			
	D -2 or D -1	D1	D2	D3	D4	D5	D6	D7	D8	D9	D10	D11	D12	D13	D14	D15 (D14 +24h)	D16 (D14 +48h)	D17 (D14 +72h)		D18 (D14 +96h)		
Bronchoscopy																X						
Adverse Event Review		←-----→																				

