10.5.4. Calculation of Spirometry Screening Parameters

- Derived parameters for spirometry data at screening will be calculated as follows:

Predicted Normal FEV₁

- Predicted Normal FEV₁ will be calculated using the working party of the European Community for Coal and Steel (ECCS) formula [Quanjer, 1993] :

$$\text{Predicted Normal FEV}_1 = b_0 * \text{Height} + b_1 * \text{Age(Yr)} + b_2$$

- The coefficients for male and female subjects are shown in Table 9. Note that no race corrections will be made.

Table 9 Predicted Normal FEV₁ Equation: Coefficients for Male and Female Subjects

	Height (b ₀)	Age (b ₁)	Intercept (b ₂)
Male	0.0430	-0.029	-2.49
Female	0.0395	-0.025	-2.60

% Predicted Normal FEV₁

$$\frac{\% \text{Predicted Normal FEV}_1}{\text{Normal FEV}_1} = \frac{\text{MaxFEV}_1}{\text{Predicted Normal FEV}_1} * 100$$

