10.11.3. Study Population Tables

Study Population Tables					
No.	Population	IDSL / TST ID / Example Shell	Title	Programming Notes	Deliverable
Part A (Single Dose Escalation): Subject Disposition					
1.101	Screened (Part A)	ES1	Summary of Subject Disposition (Single Dose)		SAC
1.102	Screened (Part A)	ES6	Summary of Reasons for Screening Failure (Single Dose)		SAC
1.103	Safety (Part A)	DV1a	Summary of Important Protocol Deviations (Single Dose)		SAC
1.104	Safety (Part A)	DV1a	Summary of All Inclusion/Exclusion Criteria Deviations (Single Dose)		SAC
Part B (Repeat Dose): Subject Disposition					
1.201	Screened (Part B)	ES1	Summary of Subject Disposition (Repeat Dose)		SAC
1.202	Screened (Part B)	ES6	Summary of Reasons for Screening Failure (Repeat Dose)		SAC
1.203	Safety (Part B)	DV1a	Summary of Important Protocol Deviations (Repeat Dose)		SAC
1.204	Safety (Part B)	DV1a	Summary of All Inclusion/Exclusion Criteria Deviations (Repeat Dose)		SAC

Study Population Tables					
No.	Population	IDSL / TST ID / Example Shell	Title	Programming Notes	Deliverable
Part A (Single Dose Escalation): Demographics					
1.105	Safety (Part A)	DM1	Summary of Demographic Characteristics (Single Dose)	Include baseline FEV1 and %predicted normal FEV1.	SAC
1.106	Safety (Part A)	DM5	Summary of Race and Racial Combinations (Single Dose)		SAC
1.107	Safety (Part A)	SA1	Summary of Study Populations (Single Dose)		SAC
Part B (Repeat Dose): Demographics					
1.205	Safety (Part B)	DM1	Summary of Demographic Characteristics (Repeat Dose)	Include baseline FEV1 and %predicted normal FEV1.	SAC
1.206	Safety (Part B)	DM5	Summary of Race and Racial Combinations (Repeat Dose)		SAC
1.207	Screened (Part B)	SA1	Summary of Study Populations (Repeat Dose)		SAC
Part A (Single Dose Escalation): Medical Condition & Con Meds					
1.108	Safety (Part A)	MH1	Summary of Current/Past Medical Conditions (Single Dose)		SAC
1.109	Safety (Part A)	CM1	Summary of Concomitant Medications (Single Dose)		SAC

Study Population Tables					
No.	Population	IDSL / TST ID / Example Shell	Title	Programming Notes	Deliverable
Part B (Repeat Dose): Medical Condition & Con Meds					
1.208	Safety (Part B)	MH1	Summary of Current/Past Medical Conditions (Repeat Dose)		SAC
1.209	Safety (Part B)	CM1	Summary of Concomitant Medications (Repeat Dose)		SAC

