10.11.13. Non-ICH Listings: Part A (Single Dose Escalation)

Non-ICH : Listings					
No.	Population	IDSL / TST ID / Example Shell	Title	Programming Notes	Deliverable [Priority]
Safety Data					
47.	Screened (Part A)	AE2	Relationship between System Organ Class and Verbatim Text (Single Dose)		SAC
48.	Screened (Part A)	Other Listing 3 in /arenv/arprod/gsk2269557/pii115117/part_a/drivers/saf_l3_cp_hm7.sas	Listing of 24 Hour Holter Findings at Screening (Single Dose)		SAC
49.	Screened (Part A)	Other Listing 2 in /arenv/arprod/gsk2269557/pii115117/part_a/drivers/saf_l2_list.sas	Listing of Cardiac Telemetry ECG Findings (Single Dose)		SAC
Pharmacodynamic Data					
50.	Screened (Part A)	PFT11	Listing of %Predicted FEV1 Data at Screening (Single Dose)	To include 'Pred. Normal' and '%Pred Normal' columns. Exclude 'Pre/Post Broncho' and '%Rev' columns	SAC
51.	Screened (Part A)	PFT9	Listing of FEV1 Data (Single Dose)	Include triplicate and maximum values.	SAC

Non-ICH : Listings					
No.	Population	IDSL / TST ID / Example Shell	Title	Programming Notes	Deliverable [Priority]
52.	Screened (Part A)	Listing 63 in /arenv/arprod/gsk2269557/pii16617/part_c/drivers/l_sputprep_partc.sas	Listing of Sputum Sample Preparation and Haemacytometry/Cytospin Preparation Data (Single Dose)	Include sputum weight and time to first induction at each timepoint	SAC
53.	Screened (Part A)	Listing 64 in /arenv/arprod/gsk2269557/pii16617/part_c/drivers/l_pip_partc.sas	Listing of Phospholipid Data in Sputum (Single Dose)		SAC
Pharmacokinetic Data					
54.	PK (Part A)	PKCL1x	Listing of Plasma GSK2292767 Pharmacokinetic Concentration-Time Data (Single Dose)		SAC
55.	PK (Part A)	PKUL2x	Listing of Urine GSK2292767 Excretion Data(Single Dose)	Highest dose only so will only be 1 period of data	SAC
56.	PK (Part A)	PKPL1x	Listing of Derived Plasma GSK2292767 Pharmacokinetic Data (Single Dose)	List all Part A PK parameters	SAC

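### Read as written, the general averaging rule puts the triplicate FEV1 summaries on a mean, while the only single FEV1 value the SAP derives elsewhere is the maximum

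*SAP*

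**What the plan says.** - **The general rule.** SAP 10.5.1, on how replicate readings are handled, says this: "Mean of the measurements will be calculated and used in any derivation of summary statistics but if listed, all data will be presented". No parameter is excepted.
- **Where it bites.** Both schedules in 10.1.1 list "Spirometry (triplicate"). Part B takes it daily on Days 1 to 14, with the note "4. Perform assessment pre dose and 1h post dose". Part A takes it pre-dose and at one post-dose time. The other scheduled physiological measures are single readings: "12-lead ECG (single") and "Vital signs (single"). Section 2.2 names spirometry as a component of the primary endpoint.
- **The summaries affected.** Table 3 (section 7.1.3) plans a change-from-baseline summary of lung function. Tables 2.113 and 2.213 deliver it from shell PD_PFT1, with blank programming notes. For Tables 1.105 and 1.205 the note is "Include baseline FEV1 and %predicted normal FEV1".
- **Where the maximum appears.** Section 10.5.4 opens "Derived parameters for spirometry data at screening will be calculated as follows" and divides MaxFEV1 by predicted FEV1. Listing 51 carries the note "Include triplicate and maximum values", and Listing 61 carries the same note for Part B.

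**The concern.** Someone programming from 10.5.1 would average the three blows. Someone programming from 10.5.4 and the FEV1 listings would take the highest. Each could defend the choice, and the two would produce different summaries of a primary safety measure. The averaging reading is the one the text supports, because the rule covers every summary statistic and nothing visible lifts it for spirometry.

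Three things would follow:

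- The summarised FEV1 would be a value that no listing is asked to show.
- Tables 1.105 and 1.205 would place a mean-based baseline FEV1 beside a maximum-based % predicted FEV1.
- The change after an inhaled dose could differ from the change in the maximum, because one low blow moves the mean and leaves the maximum untouched.

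**Working it through.** The plan states no figure on this point, so there is nothing to reproduce. The check is a trace through the text, followed by an illustration of size.

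**Trace**

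1. The rule in 10.5.1 applies to any summary statistic.
2. Section 10.5.3 (safety derivations) covers ECG, adverse events and laboratory values. It has no spirometry entry.
3. Section 10.5.4 covers predicted and % predicted FEV1, at screening only.
4. Tables 2.113 and 2.213 have no programming note, so nothing visible displaces step 1.
5. The authors did write an override where they wanted one: Tables 4.101 and 4.201 ask for the geometric mean of the sputum replicates. FEV1 has no equivalent.
6. Section 10.4.2.1 defines baseline as the latest pre-dose assessment. Under step 1 the baseline FEV1 is then also a mean of three.

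**Difference in level.** Assume three independent normal blows with within-session SD *s*. The expected maximum exceeds the expected mean by 0.846 × *s*. The plan gives no *s*; 0.05 to 0.15 L is an assumed range.

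| Assumed *s* (L) | Maximum minus mean (L) |
|---|---|
| 0.05 | 0.846 × 0.05 = 0.042 |
| 0.10 | 0.846 × 0.10 = 0.085 |
| 0.15 | 0.846 × 0.15 = 0.127 |

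**Difference in change from baseline.** The expected gap between the two rules is 0.846 × (*s* post − *s* pre). It is zero when blow-to-blow spread is the same before and after dosing. If the spread rose from 0.05 to 0.15 L, it would be 0.846 × 0.10 = 0.085 L.

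**Individual subjects.** The values below are invented to show direction only.

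| Example | Pre-dose blows (L) | Post-dose blows (L) | Change by mean | Change by maximum |
|---|---|---|---|---|
| 1 | 3.60, 3.55, 3.10 | 3.58, 3.55, 3.50 | 10.63/3 − 10.25/3 = +0.127 | 3.58 − 3.60 = −0.02 |
| 2 | 3.40, 3.35, 3.30 | 3.40, 3.20, 3.00 | 3.20 − 3.35 = −0.15 | 3.40 − 3.40 = 0.00 |

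In example 1 a low pre-dose blow makes the mean rise while the maximum falls slightly. In example 2 the mean falls and the maximum does not move.

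**Precision.** Under the same random-blow model, the variance of the mean of three is 0.33 *s*² and that of the maximum of three is 0.56 *s*².

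**The case against.** **The averaging of FEV1 is inferred.** This stands. No line says that FEV1 is averaged. The inference rests on a generic rule in a section that still contains an unfilled template entry. The PD_PFT1 shell is not shown and might specify a value, and section 10.4.3 applies the sponsor's reporting standards unless otherwise stated. But 10.5.1 does state otherwise, and a written rule should not depend on a shell to reverse it.

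**The FEV1-specific text could be read as governing.** Every FEV1 instruction that names a single value names the maximum, so a reader could take the maximum as intended throughout. That is plausible, but the explicit override for sputum replicates points the other way. At best the text is open to two readings.

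**The listings do not contradict the rule.** A reader might infer that Listings 51 and 61 use the maximum alone. They do not. They show all three blows, as 10.5.1 requires, and the maximum as well. A mean could be recomputed from them.

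**No mean-based % predicted would be printed.** A reader might infer that the rule corrupts % predicted. It does not: 10.5.4 always uses MaxFEV1 and applies to screening only. Baseline FEV1 and screening % predicted may also come from different visits, so they need not agree exactly under either rule.

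**Neither value is shown to be wrong in itself.** Example 1 depends on an invented low blow, and the documents do not say whether such a blow would be repeated. Example 2 shows that the maximum can miss a fall that the mean registers. The level gap largely cancels in change from baseline, and the mean is the more precise of the two under random error. All of this stands. The case for the maximum is therefore consistency with the plan's own FEV1 derivations; the documents do not show it to be the better measure.

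**Conclusion.** The point holds in this form: the stated rule puts the primary-endpoint FEV1 summaries on a different basis from the only single FEV1 value the plan derives elsewhere, and no visible text resolves it. This goes beyond missing detail, because following the SAP literally produces the mismatch.

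The size cannot be fixed from the document. The level differs by 0.042 to 0.127 L for an assumed within-session SD of 0.05 to 0.15 L with normal, independent blows. The effect on change from baseline may be near zero on average and can go either way in individuals.

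The consequence is limited. Spirometry is one of five primary safety components, the summaries are descriptive, and no test is planned on it. Every blow is listed, so either summary can be recovered. It should be settled before database freeze, by which time the synopsis requires final-analysis decisions to be made. A reader might go further and conclude that the mean is an error that hides airway effects; the documents do not support that.

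**What to change.** Add to 10.5.1: *Spirometry is the exception: the highest FEV1 of the triplicate at each time point is the analysis value for baseline, change from baseline and Tables 1.105, 1.205, 2.113 and 2.213.* This agrees with MaxFEV1 in 10.5.4. Keep all three blows and the maximum in Listings 51 and 61, and check that the PD_PFT1 shell says the same.

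The cost is one sentence and one derivation line. The maximum is already derived for the listings, so no new data are needed. The downside is the larger variance if blow-to-blow error is purely random (0.56 against 0.33 in units of the squared within-session SD).
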